6.5 Data management

Data from all included patients will be reported. Every year during the time of inclusion of patients to the study and the next 3 year period safety data will be reported to the authorities. After final analyses of the study the data will be stored for 15 years from inclusion of last patient in study. The data will be available for the authorities at all times.

7. Administration of drugs

7.1 Tarceva® (erlotinib)

Tarceva is an orally active, potent, selective inhibitor of the EGFR tyrosine kinase. Tarceva will be administered on an outpatient basis at a fixed dose according to schedule as a single daily oral dose. Dosage is not based upon body weight or body surface area. The Tarceva used in the study after the induction period in combination with radiotherapy will be labelled to each patient, and records of batch numbers for each patient will be kept at the pharmacy for 15 years

Prescribed daily dose is to be taken preferably in the morning, with up to 200 mL of water. Tarceva should be taken at least 1 hour before or 2 hours after the ingestion of any food or other medications, including grapefruit juice, vitamins and iron supplements.

Missed daily doses should be skipped. Doses should be taken at the same time each day. If the patient vomits after taking the tablets, the dose is replaced only if the tablet can actually be seen and counted. If a patient misses a dose normally taken in the morning, the dose should not be taken later on.

7.2 Concomitant medication

Patients with a history of dry eyes should be advised to use an ocular lubricant.

- Concomitant treatment with warfarin or coumarin-derivative is permitted provided increased vigilance occurs with respect to monitoring INR (International Normalized Ratio). However, it is recommended to use low-molecular heparin.
- Patients who receive protocol treatment should not receive any other (non-anticancer) investigational drugs until after the post-treatment assessment (at least 30 days after the final dose of protocol treatment).
- Patients who continue to wear contact lenses may have an increased risk of ocular adverse events.

7.3 Potential drug interactions

Substances that are potent inhibitors of CYP3A4 activity (eg, ketoconazole) decrease Tarceva metabolism and increase Tarceva plasma concentrations. This increase may be clinically relevant as adverse experiences are related to dose and exposure; therefore, caution should be used when administering CYP3A4 inhibitors with Tarceva.

Substances that are potent inducers of CYP3A4 activity (eg, rifampin, phenytoin) increase Tarceva metabolism and significantly decrease Tarceva plasma concentrations.

INR elevations and/or bleeding events have been reported in some cancer patients taking warfarin while on Tarceva. Patients taking warfarin or other coumarin-derivative anticoagulants should be monitored regularly for changes in prothrombin time or INR. Tobacco smoking may diminish the plasma levels of Tarceva, and may diminish the effect of radiation and should be avoided during the study period.

8. Adverse events

An AE is defined as any untoward medical occurrence in a patient or clinical investigation patient administered a pharmaceutical product regardless of its causal relationship to the study treatment. An AE can therefore be any unfavourable and unintended sign (including an abnormal laboratory finding), symptom, or disease temporally associated with the use of medicinal (investigational) product.

The occurrence of an AE may come to the attention of study personnel during study visits and interviews of a study recipient presenting for medical care, or upon review by a study monitor.

Information to be collected includes event description, time of onset, clinician's assessment of grade, relationship to study product (assessed only by those with the training and authority to make a diagnosis), seriousness, action taken with study drug, outcome, and time of resolution/stabilization of the event. All AEs occurring while on study must be documented appropriately regardless of relationship. All AEs will be followed to adequate resolution. All AEs must be reported on CRF to sponsor in order to record them for a final report to the Danish Medicines Agency.

Any medical condition that is present at the time that the patient is screened should be considered as baseline and not reported as an AE. However, if it deteriorates at any time during the study, it should be recorded as an AE.

Changes in the severity of an AE should be documented to allow an assessment of the duration of the event at each level of intensity to be performed. Adverse events characterized as intermittent require documentation of onset and duration of each episode.

8.1 Serious adverse events (SAEs)

An SAE is defined as an AE that meets one of the following conditions:

- Death during the period of protocol defined surveillance
- Life-threatening event (defined as a patient at immediate risk of death at the time of the event)
- An event requiring inpatient hospitalisation or prolongation of existing hospitalisation during the period of protocol defined surveillance with the exception of treatment-related enteritis or fatigue, leucopenia, thrombocytopenia or hospitalization due to treatment administration or other elective measures
- Results in congenital anomaly or birth defect
- Results in a persistent or significant disability/incapacity
- Any other important medical event that may not result in death, be life threatening, or require hospitalisation, may be considered a serious adverse experience when, based upon appropriate medical judgment, the event may jeopardize the patient and may require medical or surgical intervention to prevent one of the outcomes listed above. Examples of such medical events include allergic bronchospasm requiring intensive treatment in an emergency room or at home, blood dyscrasias or convulsions that do not result in inpatient hospitalisation, or the development of drug dependency or drug abuse.

In this study unexpected and related SAEs are defined as adverse reactions with at least a possible relationship to study therapy that are not consistent with the approved summary of product

characteristics (SPC) and which to their nature are serious. The SPC is available at:
www.emea.europa.eu

All SAEs will be recorded on the appropriate SAE CRF, followed through resolution by the investigator, and reviewed and evaluated by the Medical Monitor

Abnormal laboratory values and clinical adverse events will be reported as SAEs if they are graded higher than 3 on the CTC v3.0.

Any adverse event that is considered SERIOUS must be reported within one working day (IMMEDIATELY) by the investigator to the Sponsor. Sponsor must make sure that information on all suspected unexpected serious adverse reactions (SUSARs) which are fatal or life-threatening are reported as soon as possible and within 7 days to the Danish Medicines Agency after sponsor has received knowledge himself (if applicable also to local health authorities as per national regulations). All other SURSARs must be reported to Danish Medicines Agency within 15 days. All related and unexpected SAEs are also immediately reportable to Roche A/S as expedited reports:

Drug Safety Roche A/S

[contact]

[contact]/[contact]

Not immediately reportable SAE:

Progression or deterioration of the malignancy under study (including new metastatic lesions and death due to disease progression) will be part of the efficacy assessment and should NOT be reported as AE/SAE. *Signs* and *symptoms* clearly associated with the malignancy under study should NOT be reported as AE/SAE unless:

- Newly emergent (i.e. not present at baseline) and association with the underlying malignancy and old/new metastatic lesions is unclear
- If the investigator attributed deterioration of malignancy-associated signs and symptoms directly to the study drug
- Should there be any uncertainty regarding the attribution of the malignancy under study to an AE, it should be reported as an AE or a SAE accordingly.

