8.2 Expected adverse effect

Tarceva: The most common, expected adverse events for Tarceva include: Rash, pruritus, dry skin, diarrhea, nausea, vomiting, stomatitis, abdominal pain, fatigue, dyspnoe, cough, anorexia, infection, conjunctivitis, and keratoconjunctivitis sicca.

Irradiation: The toxicity of irradiation of NSCLC is determined of the dose and treatment volume of organs at risk. These are as followed:

Organs at risk	Acute (1-12 weeks)	Late >3 months
Lung ¹	Pneumonitis (cough, dyspnoe, fever)	Fibrosis (cough, dyspnoe)
Esophagus ²	Swallowing difficulties, pain	Stenosis (swallowing difficulties)
Heart	Pericarditis ⁴	Fibrosis
Skin	Edema, skin rash	Fibrosis, telangiectasies
Spinal cord	Lhermitte sign ³	Radiation myelitis ⁴ (neurological deficits)

¹: The risk of acute pneumonitis may increase in irradiation when Tarceva is combined with -radiation. The risk of pneumonitis increases with the V₂₀ of the lung. The symptoms may develop before stop of irradiation. The treatment in the case of pneumonitis is steroid ± antibiotics.

² Occurrence of esophagitis is connected to treatment volume and concomitant therapy.

³ Lhermitte sign is a transient self-limiting symptom of radiation impact on the cervical spinal cord.

⁴Pericarditis and radiation myelitis: no cases of these side effects are expected in this study.

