8.4 Management of radiation complications

In case of increasing dyspnoe during radiation or within 3 months after cessation of radiation pneumonitis must be suspected. Treatment with steroids is recommended e.g. prednisolone 25-50 mg or higher doses if necessary administered as 1-2 daily doses. Since infection is difficult to rule out, it is recommended to start treatment with antibiotics. Since tumor progression, myocardial infarction, and thromboembolic conditions may occur in these patients, ECG and appropriate biochemistry should be obtained. CT-scan or ECCO of the heart may be necessary.

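### Section 8.1 exempts progression deaths from AE/SAE reporting even inside the pneumonitis window, so a fatal lung event confidently but wrongly called progression has no written route to safety review

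*Protocol*

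**What the plan says.** Protocol section 8.1 opens with "An SAE is defined as an AE that meets one of the following conditions", and the first condition is "Death during the period of protocol defined surveillance". No exception is noted there. Recorded SAEs go to the Medical Monitor for evaluation, and clinical adverse events above grade 3 are also to be reported as SAEs.

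Further down, under the heading "Not immediately reportable SAE", the same section states that progression of the malignancy (including "death due to disease progression) will be part of the efficacy assessment and should NOT be reported as AE/SAE"). The next sentence exempts signs and symptoms clearly due to the malignancy, subject to three bullets. One keeps newly emergent signs reportable where "association with the underlying malignancy and old/new metastatic lesions is unclear". Another covers deterioration that the investigator attributes to the study drug. The last is general: "Should there be any uncertainty regarding the attribution of the malignancy under study to an AE, it should be reported" as an AE or SAE.

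Two other sections bear on this. Section 8.2 says that "The risk of acute pneumonitis may increase in irradiation when Tarceva is combined with" radiation. Section 8.4 requires pneumonitis to be suspected when dyspnoea increases during radiation or in the 3 months after it, says that infection is hard to exclude, and adds other possibilities: "Since tumor progression, myocardial infarction, and thromboembolic conditions may occur in these patients".

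**The concern.** Early respiratory death is the safety outcome that matters most when an EGFR inhibitor is added to thoracic radiotherapy. It is also the outcome in which toxicity, infection and progression are hardest to tell apart, as section 8.4 recognises. Section 8.1 lets one judgement, the site's own attribution, decide whether such a death enters the safety data, and it makes no distinction by time. A death in the fourth week of treatment is handled like one in the fourth year.

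There is no control arm in which an excess of early deaths would stand out. The one scheduled toxicity review (section 6.3, after patient 20 has one month of follow-up) can assess only what has been recorded as toxicity. At stake is whether treatment-related mortality is fully ascertained while the trial is still running.

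**Working it through.** No stated figure is in dispute, so the check is mainly a reading of the text.

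**1. Definition, heading and exception side by side**

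- Definition: an SAE is first an adverse event; death under surveillance then makes it serious.
- Heading: the events below it are SAEs whose reporting is merely not immediate.
- Text under the heading: progression and death from it are not reported as AE or SAE at all.

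The definition and the exception can be read together, the second limiting the first. The heading fits neither, and the definition does not point to the exception.

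**2. Where a death goes, by what the site believes**

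| Site's judgement | Route under 8.1 |
|---|---|
| Lung toxicity | SAE, then Medical Monitor |
| Unsure | AE or SAE, if the uncertainty bullet covers deaths |
| Confident of progression, and right | Not reported, as intended |
| Confident of progression, and wrong | Not reported; no review outside the site is written |

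The bullets hang grammatically on the signs-and-symptoms sentence, not on the sentence about death. The third is worded broadly enough to cover deaths, but the text does not say that it does. The last row is the gap, and it holds even if the bullet is read broadly.

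**3. Timing**

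Erlotinib and radiotherapy last about 6.5 weeks (section 3.2), or 1.5 months. Adding the 3 months of section 8.4 puts the end of the pneumonitis window at about month 4.5. After weekly visits during treatment there is one visit at day 30-45 after treatment (section 5.3), and the next is at month 6 (section 5.4). Scheduled follow-up also ends at recurrence (section 5.4), so a patient labelled as recurrent leaves the scheduled recording of side effects.

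**4. Upper scale of the extra reporting**

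Inputs: one-year survival 61% (section 1.1, 200 patients with stage III treated at one centre); 57 patients (section 6.2); window 4.5 months. Constant hazard is my assumption.

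- Hazard = -ln(0.61)/12 = 0.0412 per month.
- Expected deaths in the window = 57 × (1 - exp(-0.0412 × 4.5)) = 57 × 0.169 = 9.6.

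This counts deaths from every cause. Deaths that are not attributed to progression and meet the definition are SAEs already, so the number of additional forms is smaller.

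The assumption can be tested against section 1.1. It gives 9-month survival of 0.61^0.75 = 69.0%, while that section reports 70% local failure free survival at 9 months. If death counts as an event in that endpoint, survival cannot be lower than 70%, so a constant hazard slightly overstates early deaths in that cohort.

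**5. What cannot be computed**

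The number of toxic deaths missed needs the share of progression-attributed deaths that are really lung toxicity. The document gives no such share. The effect on the stopping rule in section 6.3 cannot be worked out either. More than 15% of 20 means at least 4 patients, but the rule names grade 4 pneumonitis or esophagitis and does not say whether fatal cases count.

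**The case against.** The case against is substantial, and most of it stands.

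- **No flat contradiction.** A reader might infer that every death is an SAE by definition and that the later paragraph denies this. The definition applies to adverse events, and the later paragraph is a specific exception with a stated reason: progression is assessed as efficacy. Survival is an endpoint, so the deaths themselves are still recorded. What goes unreviewed is their cause.
- **Safeguards exist.** A reader might infer that fatal lung toxicity mistaken for progression gets no safety attention at all. That goes too far. Doubtful attributions are to be reported, at least on the broad reading of the bullet. Section 8 has all AEs documented regardless of relationship, and those above grade 3 are SAEs, so lung toxicity recognised before death is reportable in its own right. Section 8.4 sets the default towards suspecting pneumonitis. Section 6.3 also allows stopping at any time for unexpected severe toxicity, and section 6.5 requires yearly safety reports.
- **Direction of bias.** A reader might infer that treatment-related mortality can only be understated. That is not shown: the uncertainty bullet and the suspect-pneumonitis rule may also move some true progression deaths into the toxicity count.
- **Size.** It is tempting to apply an assumed misattribution share to the 9.6 deaths; 10-30% would give about 1 to 3. The share has no basis in the document, and the base wrongly includes deaths that are already reportable.

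One part of the answer is incomplete. Each safeguard works only if the site doubts its attribution or recognises toxicity. None reaches a confident error.

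**Conclusion.** The point holds in a limited form. The death criterion, the heading and the exception in section 8.1 are poorly reconciled, and it is unclear whether the uncertainty bullet applies to deaths. Within the period when the protocol itself expects pneumonitis, a confident but wrong attribution to progression has no written route to the Medical Monitor or into the toxicity data for the interim committee. The likely consequence is some under-counting of treatment-related deaths. Its size cannot be derived from the document, and I put no figure on it.

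This rests on the text alone. The only number used, about 10 deaths in the window, measures the cost of the remedy. It assumes a constant hazard and that the section 1.1 cohort resembles the trial population; a higher early death rate in the trial would raise it. This is a cheap improvement in safety ascertainment. It does not affect the primary analysis.

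**What to change.** In section 8.1:

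1. Add a cross-reference from the death criterion to the progression exception, and reword the heading so that it no longer describes non-reportable events as SAEs.
2. State that the uncertainty bullet applies to deaths as well as to signs and symptoms.
3. Require every death from the first erlotinib dose to 3 months after the end of radiotherapy (the window in section 8.4) to be reported as an SAE whatever the attributed cause and whether or not recurrence has been recorded, with the cause reviewed by the Medical Monitor.
4. State that these deaths are included in the data given to the interim committee under section 6.3.
5. Keep the exemption for later deaths due to progression.

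This changes reporting only. A fixed window is one workable convention, and the document does not dictate it; items 1 and 2 are the minimum, but they would leave the confident error unseen. The cost is about one paragraph of text and, under the constant-hazard assumption, at most about 10 additional SAE forms over the trial, most of them likely for true progression.

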8.2 Expected adverse effect

Tarceva: The most common, expected adverse events for Tarceva include: Rash, pruritus, dry skin, diarrhea, nausea, vomiting, stomatitis, abdominal pain, fatigue, dyspnoe, cough, anorexia, infection, conjunctivitis, and keratoconjunctivitis sicca.

Irradiation: The toxicity of irradiation of NSCLC is determined of the dose and treatment volume of organs at risk. These are as followed:

Organs at risk	Acute (1-12 weeks)	Late >3 months
Lung ¹	Pneumonitis (cough, dyspnoe, fever)	Fibrosis (cough, dyspnoe)
Esophagus ²	Swallowing difficulties, pain	Stenosis (swallowing difficulties)
Heart	Pericarditis ⁴	Fibrosis
Skin	Edema, skin rash	Fibrosis, telangiectasies
Spinal cord	Lhermitte sign ³	Radiation myelitis ⁴ (neurological deficits)

¹: The risk of acute pneumonitis may increase in irradiation when Tarceva is combined with -radiation. The risk of pneumonitis increases with the V₂₀ of the lung. The symptoms may develop before stop of irradiation. The treatment in the case of pneumonitis is steroid ± antibiotics.

² Occurrence of esophagitis is connected to treatment volume and concomitant therapy.

³ Lhermitte sign is a transient self-limiting symptom of radiation impact on the cervical spinal cord.

⁴Pericarditis and radiation myelitis: no cases of these side effects are expected in this study.

8.3 Management of radiation complications during radiotherapy

In case of grade 3 or worse esophagitis or pneumonitis, the administration of Tarceva will be terminated for that patient.

8.4 Management of radiation complications

In case of increasing dyspnoe during radiation or within 3 months after cessation of radiation pneumonitis must be suspected. Treatment with steroids is recommended e.g. prednisolone 25-50 mg or higher doses if necessary administered as 1-2 daily doses. Since infection is difficult to rule out, it is recommended to start treatment with antibiotics. Since tumor progression, myocardial infarction, and thromboembolic conditions may occur in these patients, ECG and appropriate biochemistry should be obtained. CT-scan or ECCO of the heart may be necessary.

8.5 Management of rash inside and out side radiation field

Management of rash should be treated according to institution guidelines.

9. Ethical consideration

Patients with locally advanced non-small cell lung cancer have a very poor long-time survival as only about 15% of the patients are alive 5 years after curatively intended radiotherapy (1). A major cause of these poor results is lack of local control of the tumor after radiotherapy. Standard treatment prescribes concurrent chemo-radiation but in many cases use of concurrent chemo-radiation is not feasible. Another problem in the treatment of locally advanced NSCLC is occurrence of toxicity. There is therefore an urgent need to develop treatment that increases local control without increasing toxicity to an unacceptable level. The current study is designed to do that. The protocol fulfils the Helsinki II declaration and the national requirement to studies of

patients with a cancer disease. The patients will be fully informed about the aspects of the treatment and risk included in participating. Informed consent will be obtained after sufficient time of reflection has been given.

10. Study conduct and economy

The study is investigator initiated and will be conducted according to the ICH-CGP guidelines and according to regulatory requirements. [name] is the principal investigator (sponsor). The study is part of the Danish Center for Interventional Research in Radiation Oncology (CIRRO), protocol CIRRO IP020209. The patients will be recruited among patients referred for treatment at each participating center. Economical support of 15,000 DKK per patient included to carry out the study will be applied from the company Roche a/s, DK, which manufacture Tarceva. This support is to compensate the additional time used by the staff, primarily by research nurses, who help with registration of effects and side effects of the treatment, and the amount will be paid to the research unit at the oncology centers. There is no economical benefit for neither the department, the investigators in the study, nor the staff.

11. Publication

The study will be published in an international journal despite the result. The first draft of the manuscript will be prepared by [name]. Other members of the protocol committee will be authors if the institutions they represent include patients. Any other center including 3 patients or more will be offered authorship according to the Vancouver rules of authorship.

